10.1 Informed Consent and Screening Log

The investigator or designee must review the informed consent form (ICF) with each prospective patient to be certain that the prospective patient understands the procedures and risks of the trial. Prospective patients who wish to participate in the trial must provide written informed consent by signing the ICF before undergoing any screening procedures. Patients may undergo trial screening tests prior to giving written informed consent provided that these tests are considered part of standard care.

The information from the consent form should be translated and communicated to the patient in language understandable to the patient.

A copy of the signed and dated consent form should be given to the patient before participation in the trial. The initial ICF and any subsequent revised written ICF, and written information must receive the Institutional Review Board (IRB) approval/favorable opinion in advance of use. The patient or his/her legally acceptable representative should be informed in a timely manner if new information becomes available that may be relevant to the patient's willingness to continue participation in the trial. The communication of this information should be documented.

The investigator or designee will maintain a log of all patients who sign the ICF. At a minimum, the log will include a patient identifier, the dates of informed consent and screening procedures, the outcome of the screening, and the reason the patient did not enroll in the trial.

Additional requirements for informed consent are presented in [Section 14.3](#).

10.1.1 Eligibility

After written consent is obtained, screening procedures must be carried out per the Schedule of Trial Events ([Appendix 1](#) through [Appendix 4](#)). A patient must meet all of the inclusion criteria and none of the exclusion criteria to be eligible to participate in the trial. A copy of the pathology report confirming diagnosis of metastatic melanoma or recurrent or metastatic HNSCC must be obtained prior to enrollment. Assignment of patient number and dose is described in the Study Reference Manual.

10.1.2 Tumor Biopsy

Tumor biopsies from Lesion A (the target lesion to be injected) are required at Screening within 28 days prior to the first dose of SD-101. Two samples are required. The 2 samples can be taken as a single biopsy split into 2 samples or 2 separate biopsies and must meet the minimal sample size requirement per the study laboratory manual (ie, a minimum of 4 to 6 mm specimen, obtained via punch, core needle [14 gauge or smaller gauge needle], or surgical excision). One sample is for determining the expression level of PD-L1, and the other sample is for RNA expression profiling. The PD-L1 expression could be from an archival tissue sample of the target lesion if collected within 3 months of screening. A fresh biopsy needs to be obtained for the RNA profiling.

Subsequent tumor biopsies, which are taken after the start of study treatment, are obtained at time points specified per the schedule of trial events ([Appendix 1](#) through [Appendix 4](#)) and are collected pre-injection on treatment days or within the visit window. Two samples are required for these subsequent biopsies. A single biopsy can be split into 2 samples or 2 separate biopsies can be collected. Biopsies are required to meet the minimal sample size as indicated in the study laboratory manual. One sample will be used for immunohistochemistry and the second sample will be used for RNA expression profiling to identify and assess changes in immune cells and gene expression responses in the tumor microenvironment. Lesion A should be of a sufficient size such that the intratumoral biopsy does not compromise the investigator's ability to assess the lesion size changes per RECIST over time. If Lesion A is completely regressed, subsequent replacement lesion(s) do(es) not need to be biopsied. For Lesion A, biopsies would not be done in cases where it is judged by the investigator and in consultation with the Dynavax Medical Monitor to be not appropriate or feasible for either medical or technical reasons.

Written patient consent is required for biopsies. Tumor biopsies may be obtained via punch, core needle, or surgical excision. Biopsies should be limited to readily accessible tumor lesions (eg, skin; peripheral lymph nodes). If a core biopsy is performed, a tissue cylinder should be obtained that has proper size for histological examination and biomarker analysis (eg, immunohistochemistry of PD-L1, PD-L2, and other immunological markers; ribonucleic acid

[RNA] signature profiling), mutational load (HNSCC only), and formation of neoantigens (HNSCC only). (Details of tumor biopsy procedures including tumor biopsy processing and shipping procedures are provided in the study laboratory manual.)

Tumor biopsies should be collected prior to injection of SD-101. When collecting biopsies, local anesthetics may be used with the exception of topical anti-inflammatories or topical steroids. Local anesthetics should be given such that subsequent SD-101 administration will not result in dilution of the study drug (ie, avoid needle tracking between procedures and administer local anesthetic not directly in the tumor or away from the targeted site of intratumoral injection of SD-101).

A biopsy from a non-injected lesion and an injected lesion other than Lesion A at the same baseline and treatment time points as required for Lesion A is optional but highly desired. In addition, a biopsy of Lesion A, an injected lesion other than Lesion A, and a non-injected lesion at disease progression is optional but highly desirable. Collections are to be done pre-injection and may occur pre-injection on treatment days or within the visit window prior to treatment.

Exceptions for not performing biopsies are when there is a potential safety risk to the patient as determined by the Investigator in consultation with the Dynavax Medical Monitor.

10.2 Trial Visits

Procedures should be performed as close to the scheduled time as possible. The window for weekly study visits is ± 1 day and ± 3 days for every 3 week visits. The window for 24-hour visits is ± 3 hours. Windows for protocol specified imaging is ± 3 days. The visit schedule during the SD-101 dosing varies for the Phase 1 and Phase 2 Cohorts. After completion of SD-101 dosing (Trial Treatment Period), the visit schedule follows pembrolizumab dosing (Extended Pembrolizumab Treatment) with study visits Q3W until EOS.

A detailed outline of all scheduled trial procedures is provided in the Schedule of Trial Events ([Appendix 1](#) through [Appendix 4](#)). Procedures should be performed at the trial center where the patient is being treated. Patients who fail screening may be rescreened per approval by the sponsor.

The exact time at which a procedure is performed must be recorded in the patient's trial records or appropriate worksheet (if applicable). Any nonscheduled procedures required for urgent evaluation of safety concerns take precedence over all routine scheduled procedures.

Blood collections for safety evaluation assume priority over other procedures. Whenever possible, blood samples should be obtained by fresh peripheral venipuncture. If a patient does not have peripheral access, the sample may be collected from a central catheter immediately after

an initial withdrawal of at least 10 mL of blood; or preferably, after a series of other blood sample collections from the central catheter.

The patient will be assessed for AEs per the Schedule of Trial Events ([Appendix 1](#) through [Appendix 4](#)).

During Extended Pembrolizumab Treatment, sites will administer pembrolizumab Q3W and follow standard of care laboratory and assessment practices. Sites are required to report SAEs that occur during the Extended Pembrolizumab Treatment as described in Section 10.3.10 but are not required to document in the eCRF laboratory, imaging, or other patient assessments performed to monitor safety or to assess disease response or treatment during the Extended Pembrolizumab Treatment period.

If pembrolizumab treatment is temporarily withheld, treatment of SD-101 and pembrolizumab will start on the same day once pembrolizumab is resumed. Delayed dosing of SD-101 would be preferred over completely skipping a dose as long as the interval between SD-101 dosing is not less than 5 days with subsequent return of SD-101 dosing to per protocol schedule of events (see Section 7.6 for details regarding delayed or skipped doses). If both study drugs are on hold, the study visit(s) during the hold period may be skipped, with the exception that radiographic imaging must be performed according to schedule.

10.3 Safety Assessments

The safety assessments are listed below. The Schedule of Trial Events is provided in [Appendix 1](#) through [Appendix 4](#).

10.3.1 Medical and Medication History

Medical history includes clinically significant diseases, surgeries, cancer history, and all medications (eg, prescription drugs, over-the-counter drugs, herbal/homeopathic remedies, nutritional supplements) used by the patient within 28 days prior to the Screening Visit. Baseline melanoma and HNSCC disease status, histology, stage, and molecular profiling of genetic alterations or mutations (if available) will be recorded. Prior treatment includes treatment for the primary diagnosis, including prior systemic, radiation treatment and surgical treatment. Results from any prior genetic screening tests and any immunohistochemical (IHC) tests, such as for PD-L1, will be recorded. The date of last prior cancer treatment and the response to that treatment must be documented. Radiographic studies performed prior to trial entry may be collected for review by the investigator.

10.3.2 ECOG Performance Status Assessment

An assessment of PS will be performed using the ECOG PS scale of 0 to 5 ([Appendix 8](#)).

10.3.3 Vital Signs

Vital signs will be recorded and will include measurements of heart rate, respiratory rate, systolic and diastolic blood pressure, and pulse oximetry. Vital signs taken at injection visits will include oral temperature.

10.3.4 Physical Examinations

The investigator or qualified designee will conduct physical examinations. A complete physical examination will be conducted at Screening and EOS/Safety Follow-up Visit, and a targeted physical examination (based on interval history and/or AEs) including assessment of superficial lesions will be conducted at other visits per the Schedule of Trial Events ([Appendix 1](#) through [Appendix 4](#)).

10.3.5 Electrocardiogram

An ECG (12-lead with standard parameters of heart rate, shape, size and duration of P wave, P-R interval, QRS, QT interval, QTc interval, and T wave configuration) will be performed at Screening, after treatment on Day 15 and 29, and EOS for Phase 1 and at Screening for Phase 2. Additional ECGs should be obtained to evaluate AEs as applicable per standard of care.

10.3.6 Safety Laboratory Assessments

Laboratory assessments are listed below and will be performed according to the Schedule of Trial Events ([Appendix 1](#) through [Appendix 4](#)). Sample collections prior to injection and infusion on treatment days are preferred; however, these samples are allowed to be obtained the day prior to dosing. Routine laboratory tests (serum chemistry, hematology) for screening, including pregnancy testing may be obtained per standard of care and used for screening laboratory and determination of study eligibility as long as obtained within 28 days of first dose of pembrolizumab. Laboratories obtained within 7 days of Day 1 visit, with the exception of a CBC with ANC, do not need to be repeated on Day 1.

- Hepatitis and HIV testing at Screening Visit: serum hepatitis B, hepatitis C, and HIV testing per institutional standard of care as determined by laboratory tests for HBsAg, anti-HBc, and anti-HBs; anti-HCV; and anti-HIV -1/2, respectively

- Chemistry: sodium, potassium, chloride, bicarbonate, blood urea nitrogen (BUN), creatinine, glucose, calcium, AST, ALT, LDH, bilirubin, alkaline phosphatase, and C-reactive protein (CRP)
- Hematology: hemoglobin, hematocrit, white blood cell count with differential, and platelet count
- Thyroid function tests: free T3, free T4, and thyroid stimulating hormone (TSH)
- Coagulation: PT and aPTT
- Reserve serum aliquot specimens will be collected and stored frozen for possible future testing.
- Urinalysis with microscopy

Additional details for specific tests are provided in the Laboratory Manual.

10.3.7 Pregnancy

10.3.7.1 Pregnancy Testing

All WOCBP (as defined in Section 5.2.1) who are being considered for participation in the trial will be tested for pregnancy with a serum or urine β -hCG test within 72 hours prior to taking the first dose of trial treatment. If the urine test is positive or cannot be confirmed as negative, then a serum test is required which must be negative for the patient to enroll. Additional pregnancy testing should be scheduled per local regulations where applicable.

10.3.8 Injection-site Reaction Assessments

Assessments of injection-site reactions will be collected for a minimum of 90 minutes following each of the first 4 initial weekly SD-101 injections in Phase 1 as outlined in the Schedule of Trial Events ([Appendix 1](#) through [Appendix 4](#)) at the clinical site and as reported by the patient on the Diary Card for 7 days in Phase 1.

With Protocol Amendment 6, Diary Cards are discontinued in Phase 2; however, injection site reactions listed on the Toxicity Grading scale for Healthy Adult and Adolescent Volunteers Enrolled in Preventive Vaccine Clinical trials ([Appendix 5](#)) that persist for more than 7 days will be recorded as AEs (Section 11.1).

Prior to the first 4 initial weekly injections of SD-101 in Phase 1 ([Appendix 1](#)), patients will receive a new Diary Card with instructions to measure and record local injection-site reactions and solicited AEs that occur post SD-101 injection. The completed Diary Cards will be reviewed with the patients at their next study visit.

For the first 4 weekly injections of SD-101 in the first course in Phase 1, Dynavax will capture all injection-site reactions that occur, even if the diameter of the largest dimension does not meet a Grade 1 on the severity scale ([Appendix 5](#)). As such, any reaction smaller than this size cannot be graded, but will still be recorded in the clinical database and the severity will be marked as *not applicable (N/A)*.

All data documented by the patient on Diary Cards will be collected, reviewed by the trial nurse/coordinator with the patient, and recorded on the appropriate CRF.

Injection-site reactions need to be recorded also on the AE eCRF for the following:

- 1) The duration of the injection-site reaction exceeds 7 days
- 2) The verbatim term for the injection-site reaction is different than the terms listed for the diary and provided for recording on the injection-site reaction eCRF
- 3) The injection-site reaction qualifies as an SAE.

10.3.9 Adverse Events

All AEs, as defined in Section [11.2](#), will be evaluated from immediately after the first trial treatment on Day 1 through 28 days after last dose of trial treatment.

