- 3) Objective responses were observed at SD-101 dose range of 1.0 mg – 8.0 mg in anti-PD-1/L1 inhibitor naïve patients, with tumor shrinkage at the injected and non-injected lesions.
- 4) A single patient responded and durable stable disease was seen at the 8.0 mg dose in anti-PD-1/L1 inhibitor experienced patients.
- 5) There were no DLTs.
- 6) SD-101 administered intratumorally in combination with IV pembrolizumab demonstrated no worsening of the expected toxicities of each of the individual monotherapies. The most common ($\geq 20\%$) treatment-related AEs were transient low-grade fatigue, myalgia, headache, chills and injection site reactions. Grade ≥ 3 treatment-related AEs were observed in 59.1% patients (most common: myalgia 13.6% and injection site pain 13.6%). Immune-related AEs occurred in 2 patients (2/22 or 9%).

One had a Grade 2 pneumonitis on Day 23 resulting in drug withdrawal and the other had hypophysitis (85 days after last treatment).

Based on preliminary review of the data, the efficacy of 2.0 mg per lesion was higher than 8.0 mg in one lesion in patients who are naïve to anti-PD-1/L1 and the RP2D was updated to 2.0 mg in 1 to 4 lesions and/or regions. The study with the new dosing of 2 mg per injection is ongoing also in patients who are resistant/refractory to anti-PD1/PD-L1 therapy.

A summary of the clinical studies conducted to date with SD-101 is provided in the Investigator's Brochure.

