It is at the discretion of the investigator whether to continue a patient on study treatment until repeat imaging is obtained. If repeat imaging confirms PD, patients will be discontinued from the study.

Two dosing delays of pembrolizumab due to toxicity will be permitted. In the event of a third occurrence of a toxicity which would require dosing delay, pembrolizumab will be discontinued permanently.

If a subject resumes pembrolizumab treatment after a dose interruption, the interval between pembrolizumab dosing should not be less than 3 weeks (\pm 3 days) with subsequent return of pembrolizumab dosing to per protocol schedule of events.

Dosing interruptions for SD-101 or pembrolizumab are permitted in the case of medical/surgical events. For Phase 2, dosing interruptions for logistical reasons not related to study therapy (eg, elective surgery, unrelated medical events, patient vacation, and/or holidays) are permitted. Patients should be placed back on trial treatment within 3 weeks of the scheduled interruption, unless otherwise discussed with the Dynavax Medical Monitor.

The reason for any interruption in treatment should be documented in the patient's study record.

7.7 Dose Modification and Toxicity Management for Immune-Related Adverse Events Associated With Pembrolizumab

Adverse events associated with pembrolizumab exposure may represent an immunologic etiology. These immune-related AEs (irAEs) may occur shortly after the first dose or several months after the last dose of pembrolizumab treatment and may affect more than one body system simultaneously. Therefore, early recognition and initiation of treatment is critical to reduce complications. Based on existing clinical study data, most irAEs were reversible and could be managed with interruptions of pembrolizumab, administration of corticosteroids and/or other supportive care. For suspected irAEs, ensure adequate evaluation to confirm etiology or exclude other causes. Additional procedures or tests such as bronchoscopy, endoscopy, or skin biopsy may be included as part of the evaluation. Based on the severity of irAEs, withhold or permanently discontinue pembrolizumab and administer corticosteroids. Dose modification and toxicity management guidelines for irAEs associated with pembrolizumab are provided in [Table 7-1](#).

Table 7-1: Dose Modification and Toxicity Management Guidelines for Immune-related Adverse Events Associated with Pembrolizumab

General instructions:

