10.3.10 Serious Adverse Events

All SAEs, as defined in Section [11.3.1](#), will be evaluated from the time the consent is signed through 90 days following cessation of trial treatment or EOS (whichever is later), or 28 days following cessation of trial treatment if the patient initiates new anti-cancer therapy. Any SAE must be reported to Dynavax or its designee within 24 hours of the knowledge of the event.

An SAE, whether assessed as related or not related to study treatment, will be followed until considered stable, resolved, or until EOS, or the patient initiates new anti-cancer therapy (whichever is earlier).

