11.2 Adverse Events

An AE is any untoward medical occurrence associated with the use of a drug, whether or not considered drug-related. An AE can therefore be any unfavorable and unintended sign (including a clinically significant abnormal laboratory finding), symptom, or disease temporally associated with the use of a medicinal (investigational) product, whether or not related to the trial treatment.

Medical conditions present at Screening (ie, before informed consent is obtained) or present before the first trial treatment (Day 1) are not AEs and are not recorded on the AE CRF. These medical conditions should be adequately documented on the Medical History CRFs. Any increase in severity or frequency of a medical condition documented as medical history after the first trial treatment will be recorded as an AE and will be captured on the AE CRF.

Progression of the cancer under study is not considered an AE or SAE and should not be reported as an AE or SAE.

An uncomplicated pregnancy is not an AE or SAE and should not be reported as an AE/SAE. Patients should be followed as described in Section 11.5.

The reporting period for all non-serious AEs begins at the time of the first trial treatment (Day 1) through 28 days after last dose of trial treatment. Patients who are withdrawn due to an AE should have an AE assessment completed 28 days or more after their last trial treatment. All AEs will be captured on the AE CRF.

AEs should be documented in terms of a single medical diagnosis. When this is not possible, the AE should be documented in terms of signs and/or symptoms observed by the investigator or reported by the patient at each trial visit.

The investigator will follow all related AEs observed during the trial until the AEs are considered resolved or until 28 days after last dose of trial treatment or the patient begins new anti-cancer therapy, whichever is earlier. Dynavax or the Dynavax designee may request additional follow-up on specific unresolved events.

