NOTE: As of Amendment 9, Phase 2 of the trial has been modified to continue dosing per protocol; however, efficacy and exploratory endpoints will no longer be collected, and the collection of safety endpoints has been simplified. The final study visit will be the EOS/Safety Follow-up. All other procedures to monitor disease progression and safety should be performed at the investigator's discretion according to local standard of care; these data do not need to be collected on the CRE. This Schedule of Trial Events has been amended and assessments that are no longer required have been deleted.

Screening Through Day 358

Trial Period:	Screening	Trial Treatment																						
		(every week ± 1 day)					(every 3 weeks ± 3 days)					(every 3 weeks ± 3 days)												
Day:	-28 to -1 ^a	1	8	9 ^{b,cc}	15	22	29	43	64	85	106	127	148	169	190	211	232	253	274	295	316	337	358	
Study Procedures																								
Informed consent	X																							
Inclusion/Exclusion Criteria	X																							
Demographics/Medical history/Prior medications ^g	X	X																						
Vital signs ^h	X	As of Amendment 9, per local standard of care at the discretion of the investigator.																						
Physical examination ⁱ	X																							
ECOG Performance Status	X																							
12-Lead ECG ^j	X																							
Review AEs ^k		X	X	X	X	X		X	X	X	X	X	X	X	X	X	X	X	X	X	X	X	X	
Review SAEs	X	X	X	X	X	X		X	X	X	X	X	X	X	X	X	X	X	X	X	X	X	X	
Concomitant medications ^l	X	X	X	X	X	X		X	X	X	X	X	X	X	X	X	X	X	X	X	X	X	X	
HIV, HPV status, and hepatitis testing ^m	X																							

APPENDIX 4: SCHEDULE OF TRIAL EVENTS (PHASE 2 EXPANSION COHORTS 5 AND 6 [ANTI-PD-1/L1 NAÏVE] AND COHORTS 7 AND 8 [ANTI-PD-1/L1 REFRACTORY OR RESISTANT]) (CLOSED) (CONT'D)

Screening Through Day 358 (Cont'd)

Trial Period:	Screening	Trial Treatment																					
		(every week ± 1 day)					(every 3 weeks ± 3 days)					(every 3 weeks ± 3 days)											
Day:	-28 to -1 ^a	1	8	9 ^{b, ee}	15	22	29	43	64	85	106	127	148	169	190	211	232	253	274	295	316	337	358
Serum chemistry and CRP ⁿ	X	X	X		X	X		X	X	X	X	X	X	X	X	X	X	X	X	X	X	X	X
Hematology ^o	X	As of Amendment 9, per local standard of care at the discretion of the investigator.																					
Coagulation ^p	X																						
Thyroid function tests ^q	X																						
Urinalysis with microscopy																							
Pregnancy testing ^r	X																						

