APPENDIX 1-4 FOOTNOTES (CONT'D)

Review AEs ^k	In Phase 1, assessments of injection-site reactions will be collected for a minimum of 90 minutes through the first 4 weekly injections and for 30 minutes following the remaining injections of SD-101 at the clinical site. Injection-site reactions will be graded based on the Toxicity Grading Scale for Healthy Adult and Adolescent Volunteers Enrolled in Preventive Vaccine Clinical Trials (Appendix 5). In Phase 2, injection-site reactions that persist for more than 7 days will be recorded as AEs. All other AEs and laboratory safety measurements will be graded per NCI CTCAE Version 4.03. All AEs, whether gradable by CTCAE or not, will also be evaluated for seriousness. AEs will be collected through 28 days after the last dose of trial treatment.
Concomitant medications ^l	All concomitant medications taken by the patient from Screening through the EOS visit will be reported.
HIV and hepatitis testing ^m	Serum hepatitis B, hepatitis C, and HIV testing as determined by laboratory tests for HBsAg, anti-HBc, and anti-HBs; anti-HCV; and anti-HIV -1/2, respectively. For HNSCC patients only, HPV status (positive + or negative) at Screening will be determined from either archival test results or new testing.
Serum chemistry and CRP ⁿ	Per local standard of care at the discretion of the investigator.
Hematology ^o	Per local standard of care at the discretion of the investigator.
Coagulation ^p	Per local standard of care at the discretion of the investigator.
Thyroid function tests ^q	Per local standard of care at the discretion of the investigator.
Pregnancy testing ^r	For WOCBP, serum or urine pregnancy test must be negative within 72 hours prior to the first trial treatment. If the urine test is positive or cannot be confirmed as negative then a serum test is required which must be negative for the patient to enroll. Dipstick can be used. Additional pregnancy testing should be scheduled per local regulations where applicable. All female patients are considered to be WOCBP except if they have been postmenopausal for at least 2 years or surgically sterile for at least 1 year.
Blood for IFN-alpha inducible gene expression (pharmacodynamic) ^s	Phase 1 Dose Escalation Cohorts 1-4 only: IFN-inducible gene expression measured at pre-dose on Day 1 (baseline), at Day 8 prior to injection, and at Day 9 which is 24 hours after injection.

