7.0 DEFINITIONS, COMPUTATIONS, AND CONVENTIONS

7.1 Definitions and Computations

Study Day

Study day will be calculated in reference to the date of first dose (Day 1). For assessments conducted on or after the first dose date, study day is calculated as (assessment date – first dose date + 1). For assessments conducted before the first dose date, study day is calculated as (assessment date – first dose date). There will be no Day 0.

Date of First Dose and Date of Last Dose of Study Drug

The date of the first dose of study drug is defined as the date a patient receives the first dose of the study drug. The date of the last dose of study drug is the date a patient receives the last dose of the study drug.

Treatment-Emergent Period

Treatment-emergent periods are updated from what were described in the protocol (sections 10.3.9 and 10.3.10) to cover the maximum possible reporting periods.

Treatment-emergent period for AEs is defined the date and time of the first dose of study drug administration through 90 days after last dose of study drug administration.

Treatment-emergent period for SAEs is defined as the date and time of the first dose of study drug administration through EOS.

Baseline Value and Post-baseline Value

Unless otherwise specified, the baseline value is defined as the last measurement before the first dose (date and time) of study drug. Post-baseline value is defined as a measurement taken after the first dose of study drug. Change from baseline is defined as (post-baseline value – baseline value). Both date and time of study drug administration and measurement

will be considered when calculating baseline value. If time is not available, then date only will be used.

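### The SAP counts adverse events to 90 days after the last dose, but the protocol collects new non-serious events only to 28 days, so the TEAE and immune-related TEAE tables mix two levels of ascertainment

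*Protocol*

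**What the plan says.** The protocol gives one limit for non-serious events in several places. Section 10.3.9 says AEs "will be evaluated from immediately after the first trial treatment on Day 1 through 28 days after last dose of trial treatment". Section 11.2 says "The reporting period for all non-serious AEs begins at the time of the first trial treatment (Day 1) through 28 days after last dose". The footnotes to Appendices 1 to 4 say "AEs will be collected through 28 days after the last dose of trial treatment". Section 11.2.1 applies the same 28 days to non-serious events of clinical interest, and that list holds only overdose and a hepatic laboratory criterion, not immune-related AEs.

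SAEs have a longer window in Section 10.3.10: from consent "through 90 days following cessation of trial treatment or EOS (whichever is later"), shortened to 28 days after cessation if the patient starts new anti-cancer therapy. No contact is scheduled after the visit at 28 (±3) days: Appendices 2 to 4 state "The final study visit will be the EOS/Safety Follow-up".

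On timing of risk, Protocol 7.7 says immune-related AEs "may occur shortly after the first dose or several months after the last dose of pembrolizumab treatment". Protocol 2.6 reports immune-related AEs in 2 of 22 patients. One was a pneumonitis on Day 23; "the other had hypophysitis (85 days after last treatment").

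SAP 7.1 says it departs from Protocol 10.3.9 and 10.3.10 so as to take in the longest windows that could apply. Its definition reads: "Treatment-emergent period for AEs is defined the date and time of the first dose of study drug administration through 90 days after last dose". The SAE period in the same section ends at EOS. SAP 9.7.3 tabulates all TEAEs, serious TEAEs and immune-related TEAEs using these periods.

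**The concern.** Widening an analysis window does not collect more data. After post-treatment Day 28 a site that follows the protocol has no duty to record a new non-serious event and no visit at which to ask about one. Two other sources that might reveal such an event do not help. Concomitant medication recording also stops at 28 days (Protocol 10.3.11), and SAP 9.7.4 drops laboratory listings on the ground that important findings are in the AE data.

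A reader of the SAP 9.7.3 tables would see one rate labelled treatment-emergent and defined to 90 days. Part of it comes from full AE ascertainment and part essentially from SAE reporting. Compared with a full 90-day count, this incompleteness can only lower the rate. The effect falls on the kind of event for which the protocol expects late onset and promises special attention (Section 9.0). Since Amendment 9, safety is the only Phase 2 endpoint family still collected (Protocol 4.3.2.2), which makes the labelling of these tables more important.

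**Working it through.** **Inputs.** Non-serious AE collection: 28 days after last dose (Protocol 10.3.9, 11.2, 11.2.1, Appendix footnotes). SAE collection: 90 days or EOS, the later, or 28 days with new therapy (10.3.10). SAP treatment-emergent period: 90 days for AEs, EOS for SAEs (SAP 7.1). Late event: 85 days (Protocol 2.6). Last scheduled pembrolizumab dose: Day 715 (Protocol 9.2, Appendices 2 to 4).

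**The plan's own figure.** 2/22 = 9.1%, which agrees with the stated 9% (exact 95% CI 1.1% to 29.2%).

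**Gap between the windows.** 90 − 28 = 62 days. As a share of the post-treatment period, 62/90 = 68.9%; new non-serious AEs are collected for 28/90 = 31.1% of it. As a share of the whole SAP window the gap is 62/(L + 90), where L is the study day of the last dose. For L = 715 this is 62/805 = 7.7%. For a patient who stops after one dose (L = 1) it is 62/91 = 68.1%. The 69% figure therefore describes the post-treatment period only.

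**The late event.** 85 − 28 = 57 days beyond the non-serious limit and 90 − 85 = 5 days inside the SAP limit, if the 85 days run from the last dose of either drug. One late event in 22 is 4.5% (exact 95% CI 0.1% to 22.8%).

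**Collection set against analysis, by type of event (days after last dose):**

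| Event | Collected under the protocol? | Treatment-emergent under SAP 7.1? |
|---|---|---|
| New non-serious AE, day 20 | Yes | Yes |
| New non-serious immune-related AE, day 40 | No | Yes |
| New SAE, day 60, no new therapy | Yes | Yes under the AE period; under the SAE period it depends on the meaning of EOS |
| New SAE, day 60, new therapy begun day 35 | Not required | As above; SAP has no new-therapy cut-off |
| Known related non-serious AE that worsens, day 40 | Unclear: 11.4.2 follows to resolution or trial termination, 11.2 stops at 28 days or new therapy | Yes, since SAP 9.7.3 counts worsening |

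The second row is the gap. The last row is why the Days 29 to 90 data are essentially, not strictly, serious-only.

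**The SAE endpoint.** If EOS is the visit (the reading in the SAP abbreviation list), the SAE period ends 25 to 31 days after the last dose. That is 59 to 65 days short of both the protocol's 90-day SAE window and the SAP's own AE period. If EOS is the last visit of the last participant (Protocol 4.7), the period is longer for most patients. The SAP does not say which is meant.

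**The case against.** The strongest reply is that the 28-day non-serious and 90-day serious split is a deliberate design, stated consistently, and that Amendment 9 chose to simplify safety collection. Important late events can still be reported as medically significant SAEs (Protocol 11.3.1), and investigators must alert the sponsor to anything unusual (Protocol 11.0). On this view SAP 7.1 simply casts a wide net over whatever was recorded, and openly says that it departs from the protocol. This stands as a defence of the collection window, so the required change is to the analysis. It does not defend a single table whose period suggests equal ascertainment throughout; the SAP plans no split or footnote.

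A second reply is that Protocol 11.4.2, and the provision in 11.2 for later assessment of patients withdrawn for an AE, extend follow-up. They do so for known events or for withdrawn patients. Neither moves the onset limit for new non-serious AEs.

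A third reply is that the SAP was written to Amendment 8, while the protocol reviewed is Amendment 9. The Amendment 8 windows are not available, so earlier data may have been collected under different limits. That caveat stands.

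A reader might also infer from the hypophysitis that the trial has already missed late immune toxicity. The documents do not support this. The event was recorded. Its seriousness is not stated, and if serious it was within the SAE window. Nor is it said whether last treatment means SD-101 or pembrolizumab; SD-101 can end well before pembrolizumab (Protocol 7.2), in which case the event might not be post-treatment at all. The opening of that list in Section 2.6 was not in the copy used here, so attribution to this trial's Phase 1 is inferred from the combination, the dose range and the RP2D text.

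**Conclusion.** The point holds as a mismatch between collection and analysis. Run as written, SAP 9.7.3 gives 90-day TEAE and immune-related TEAE rates that are complete for new non-serious events only to Day 28, and that undercount late non-serious immune-related AEs. The conclusion rests on the stated windows and on Protocol 7.7, not on the single late event, which shows only that late onset occurs.

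The size is 62 of 90 post-treatment days, but as little as 7.7% of the whole SAP window for a patient dosed to Day 715. The number of missed events cannot be estimated reliably. One could multiply 1/22 by the 260 planned Phase 2 patients: 260 × 0.0455 = 11.8, with limits 0.3 to 59.4 from the exact interval. That should not be read as an expected loss. It rests on one event, uses planned rather than actual enrolment, and assumes that the event was non-serious and followed the last dose of both drugs.

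The unclear SAE endpoint in SAP 7.1 is a related fault, because under the visit reading serious events after about Day 28 could drop out of the serious TEAE tables. Both should be corrected before database lock; neither shows that collection under the protocol was unsound.

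**What to change.** **SAP 7.1 and 9.7.3.** Run the primary TEAE and immune-related TEAE tables through 28 days after the last dose of trial treatment, which is the protocol's collection window. Report Days 29 to 90 separately, censored at the start of new anti-cancer therapy, with a label such as: *systematic collection of new SAEs only, plus any recorded worsening of known AEs*.

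**SAP 7.1, SAE period.** Replace the EOS endpoint with the window in Protocol 10.3.10 (90 days or EOS, the later, with the new-therapy cut-off), and say which meaning of EOS applies.

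The cost is a short SAP revision, one split in the TEAE tables and a footnote. No new data are needed.

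**Optional, for patients still on treatment.** Amend Protocol 10.3.9, 11.2 and 11.2.1 to collect immune-related AEs of any seriousness over the existing SAE window, with the same new-therapy cut-off so that events after a later therapy are not counted. The cost is a short amendment and a few more AE records. The benefit is limited to patients not yet past the window, a number the documents do not give, so this step is debatable in a closed and deliberately simplified trial. The SAP changes stand without it.
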